4.5 Renal Denervation Procedure

For patients randomized to receive the renal denervation procedure, the procedure should be completed per the institution's standard of care and the study device Instructions for Use.

Procedural data collected will include but is not limited to:

- EnligHTN™ Renal Denervation System device information
- Guiding catheter used manufacturer
- Number of arteries ablated
- Number of ablations performed
- Device settings
- Procedure time
- Ablation time
- Fluoroscopic time
- Volume of contrast media

4.6 Blanking Period

For three months following the ablation procedure, the subject is in a blanking period while the cardiac tissue recovers from the RF energy application. The AF recurrences during the blanking period will not be reported. If recurrence occurs after the blanking period, the subject will be considered a 'recurrence' according to the primary efficacy endpoint.

4.7 Recurrence of AF

Recurrence is defined as documented atrial fibrillation episode lasting ≥ 30 seconds. An episode of only atrial flutter or an atrial tachycardia will be considered an episode of AF for purposes of recurrence (episodes must be documented and be ≥ 30 seconds in duration). Episodes on 12-lead ECGs are an exception and do not require a ≥ 30 second recording period to be considered a recurrence.

4.8 Re-treatment of AF

Subjects experiencing recurrent atrial arrhythmias may be treated with up to two repeat ablation procedures during the course of the 24 month study. This includes ablation of cardiac arrhythmias that may be responsible for initiating or maintaining atrial fibrillation. The subject's follow-up window will not be re-set, but there will be a 3 month blanking period following the retreatment procedure.

Re-treatment procedures will follow the ablation procedure as outlined previously in section 4.4, but additional information regarding the completeness of the initial ablation lesions will be recorded. Specifically, entrance and exit block from the pulmonary veins and completeness of any additional lesions lines that were placed will be recorded prior to any new RF energy being delivered. Pre-procedure requirements are at the discretion of the Investigator.

Repeat ablation procedures will count towards the recurrence but will not reset the follow up period. Such patients will continue to be a part of the study and adverse event data will be collected on them throughout their participation in the study.

4.9 Discharge

Prior to discharge, procedures following the center's standard of care post cardiac ablation will be performed.

For all patients, following the ablation procedure(s), the subject's blood pressure will be monitored every 4 hours post procedure until discharge, or for a maximum of 24 hours. At discharge a physical assessment will be performed and the subject's medication regimen will be reviewed and recorded. The patient will also either be given an event recorder or a 7-day holter upon discharge. Discharge is expected to occur ≤72 hours post procedure.

All new adverse events and adverse device effects since enrollment of the subject into the study will be documented on an Adverse Event CRF. The event shall be documented in source documentation and reported according to specifications in section 5.7.

4.10 Follow-up visits

Subjects will return for follow-up at 1 month (\pm 7 days), 3 months (\pm 10 days), 6 months (\pm 14 days) post procedure and annual follow-up visits at 12 (\pm 21 days) and 24 months post-procedure (\pm 60 days).

The following will be evaluated / reviewed according to Table 1:

4.10.1 Physical Assessment

The subject will have a physical assessment at every follow up visit to capture weight.

4.10.2 Medications

Medications will be recorded in addition to documenting changes to medications at each followup visit.

4.10.3 Office Blood Pressure

Office Blood Pressure measurements will be recorded as the average blood pressure of three measurements at each follow-up visit. Measurements should be taken according to Standard Joint National Committee VII Guidelines / ESC and ESH Guidelines ^{26,27} (Refer to Appendix A for Office Blood Pressure instructions).

4.10.4 24 hour Ambulatory Blood Pressure

24 hour Ambulatory Blood Pressure measurements should be taken according to Standard Joint National Committee VII Guidelines / ESC and ESH Guidelines ^{26,27}(Refer to Appendix B for 24 Hour Ambulatory Blood Pressure instructions) at 6M, 12M, and 24M follow-up visits.

In addition to the daytime mean ABP, the night time mean, and 24 hour average ABP value will be collected. When using ABP ensure that at least two measurements per hour are taken during the person's usual waking hours (for example, between 08:00 and 22:00) and 1 measurement per hour is taken during the person's usual night time hours. The average value of at least 14 measurements taken during the person's usual waking hours should be used for calculation of mean daytime value.

4.10.5 Blood and Urine Analysis

Blood and urine samples will be collected and analyzed as listed below for the renal denervation study cohort

- Serum Creatinine to be collected at 6M, 12M, and 24M follow-up visit.
- Estimated GFR (eGFR) to be collected at 6M, 12M, and 24M, follow-up visit.
- Hemoglobin A1c to be collected at the 6M follow-up visit only
- Fasting glucose to be collected at the 6M follow-up visit only
- Fasting insulin to be collected at the 6M follow-up visit only
- Urine albumin to creatinine ratio to be collected at the 6M, and 24M follow-up visit.

A true numeric value for the estimated GFR must be provided. If your site's laboratory does not report the eGFR value beyond 60 mL/min/1.73 m² the center should use a sponsor-approved calculation tool to generate the value. The sponsor will provide an approved website(s) for this calculation to study centers.

4.10.6 Echocardiogram (TTE)

Transthoracic-echocardiogram (TTE) examinations will be conducted at the 1M, 6M, 12M and 24M, follow-up visits. Each site is responsible for performing the echocardiogram per each institutions standard of care echo protocol.

4.10.7 NYHA Assessment

NYHA Assessment⁵⁷ will be evaluated at the 1M, 6M, 12M and 24M follow-up visit and should be classified based on the definitions in Appendix C.

4.10.8 EQ-5D 5L Quality of Life Questionnaire

EQ-5D 5L and AFEQT questionnaires will be completed at 1M, 6M, 12M and 24M follow-up visit.

4.10.9 Renal artery evaluation

The renal artery evaluation will only be done in subjects who underwent the renal denervation ablation procedure.

Renal artery evaluation will be completed at the 6M and 12M follow-up visits. This evaluation can be completed by either: computed axial tomography (CT scan), duplex ultrasonography, Doppler, angiography, magnetic resonance (MR) angiography or non contrast magnetic resonance imaging.

If a renal artery evaluation is completed at any other time point during the study, this data will also be collected in the Renal Artery Evaluation CRF.

4.10.10 Assessment of AF Recurrence

Assessment of AF Recurrence will be completed at the 3M, 6M, 12M and 24M follow-up visits viaevaluation of 12 lead ECG recordings, holter monitoring and/or event recorder results. Subjects will be provided 7-day holter monitors for each of these visits or implanted with an event recorder which will be evaluated for the specific 7 day period coinciding with a visit. AF recurrence will not be counted within a 3 month blanking period following the cardiac ablation procedure.

AF Recurrence is defined as episodes lasting longer than 30 seconds in duration. To count as a study-related recurrence, the AF episode must be documented. For this study, AF also includes (documented ≥30 seconds) atrial flutter and atrial tachycardia.

4.10.11 Adverse Events

Report any adverse events and adverse device effects since the last visit and document in source documents. Report the adverse event according to specifications in section 5.7.

4.11 Clinical Investigation Termination

Each subject will be followed for 2 years post ablation procedure or until time of death, loss to follow up, withdrawal or clinical investigation termination. The clinical investigation will be complete after all follow-up visits are performed, all data is received by the Sponsor and the database is locked. The study will be closed when a final report is written on the conclusions and analysis of the data.

Participation in this clinical investigation is voluntary. Subjects are free to withdraw from the clinical investigation at any time without reason. However, subjects should be strongly encouraged to complete the protocol required follow up. Should a subject wish to withdraw prior to completing 60-month follow-up, the investigator should request the subject to come in for a final visit and a Termination CRF should be completed by the site and provided to the Sponsor.

At this visit the subject should undergo the following evaluations:

• Office Blood Pressure measurement

- Blood/Urine labs
- 12 Lead ECG

In a situation where a clinical investigation withdrawal is due to an adverse event the subject should be followed until resolution of that adverse event or determination that the subject's condition is stable. Upon withdrawal from the study, data will cease to be collected on Case Report Forms.

Subjects must be informed about their right to withdraw from the investigation at any time and for any reason without sanction, penalty or loss of benefits to which the subject is otherwise entitled and withdrawal from the investigation will not jeopardize their future medical care or relationship with the investigator. Subjects will be asked to specify the reason for the withdrawal, but have the right not to answer.

The investigator may decide to withdraw a subject from the investigation at any time. The subject's future care will not be influenced by a decision, voluntary or otherwise, to withdraw from the investigation. All reasonable efforts should be made to retain the subject in the clinical investigation until completion of the investigation.

Reasons for termination include, but are not limited to, the following:

- Subject did not meet the inclusion/exclusion criteria
- Subject requests to be withdrawn from the study
- Investigator withdraws subject from the study
- Subject lost to follow-up, defined as the following: a subject will be considered
 follow-up" after a minimum of 2 documented phone calls of a physician or delegate at the
 study site to the subject or emergency contact and a certified letter sent to the last known
 address
 - Subject death (in case of subject death, cause must be documented)
 - Subject non-compliance
- Study terminated at the local, national, or international level, at the request of Ethics Committees, regulatory authorities, or SJM.
- Subject completed study

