5.7.7 Anticipated Serious Adverse Device Effect (ASADE)

A serious adverse device effect which by its nature, incidence, severity or outcome has been previously identified in the risk analysis report.

5.7.8 Procedure for assessing, recording and reporting adverse events, adverse device effects, serious adverse events and serious adverse device effects:

Safety surveillance and reporting will be done for all subjects enrolled in this investigation as described below.

Safety surveillance within this investigation and the safety reporting performed by the investigator, starts as soon as the subject is enrolled in this investigation (date of signature of the informed consent). The safety surveillance and the safety reporting will continue until the last

investigational visit has been performed or the subject is deceased or the subject/investigator concludes his participation into the investigation.

For the purpose of this trial, all Serious Adverse Events and all Adverse Device Effects (regardless of severity) are to be documented and reported to the sponsor immediately and this no later than 72 hours after becoming aware of the event.

Adverse events will be assessed by the investigator for relationship to the device and to the procedures involved.

- Procedure related: The AE is deemed related to the procedure if it occurred during the procedure but was not directly caused by the medical device.
- Device related: The AE is deemed device related if it was directly caused by the medical device.

Investigators are responsible for promptly reporting all SAEs and ADEs to the sponsor by completing the Adverse Event form. All unresolved AEs should be followed by the investigator until resolution is reached.

Note: Refer to Table 1 'Data Collection' and Appendix G 'Data Collection Method'. In case of EDC failure, notify Sponsor via Fax ([contact]) or via [contact].

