#### 2.5 The Secondary objectives

#### 2.5.1 Safety Acute data

The major adverse cardiac events (MACE) within 7 days post procedure will be summarized as a percentage of patients as defined as:

Number of subjects with major adverse cardiac events within 7 days post procedure Number of subjects with at least 7 days of follow – up or who experienced an event \* 100

The denominator includes subjects who either had an event within 7 days post procedure or were eligible to meet the endpoint, i.e. followed through at least 7 days.

The peri-procedural events will be summarized as a percentage of patients as described below. Rates will be calculated for each randomization arm.

Number of subjects with at least one event within 30 days post procedure Number of subjects with at least 30 days of follow – up or who experienced an event \* 100

All serious and possibly device or procedure related adverse events are reported and adjudicated by an internal medical expert. An event is considered a MACE if it meets the criteria defined in the Adverse Event Adjudication Plan.

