#### 2.5.2 Safety Midterm (6 months) and Long term (1-2 years) data

For all patients, the major adverse cardiac events will be recorded and summarized at 6 months, 1 year, and 2 years. Event rates will be calculated for each arm as the number of subjects who experienced a major adverse cardiac event over the number of subjects who experienced an event within or were followed to each time interval. Kaplan-Meier analysis may be performed for time to first major adverse cardiac event. For patients undergoing the renal denervation procedure:

The new (or worsened) renal artery stenosis (>50%) and/or aneurysm at the site of

- ablation per Renal Artery Imaging will be summarized at 6 and 12 months. A percentage of patients who have new stenosis and/or aneurysm compared to baseline will be provided. The denominator includes subjects with a baseline and follow-up assessment at the corresponding interval. Image interpretation will be based on local analysis. Kaplan-Meier analysis may be performed if applicable on the time to the first new renal artery stenosis and/or aneurysm at the site of ablation.
- Renal function change based on eGFR will be summarized by computing the change of the eGFR at 6 months, 12 months and 2 years compared to baseline (follow-up interval baseline) for each patient with data available in both time points. The mean and standard deviation of the eGFR change at those intervals will be presented.
- Overall renal vascular safety will be summarized as a rate of subjects with a serious, device or procedure related event over total subjects randomized to the renal denervation group at each follow-up time point.

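### Protocol 4.11 stops CRF data at withdrawal while requiring follow-up of the adverse event that caused it, so the outcome and any later worsening of an event ongoing at withdrawal are lost

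*Protocol*

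**What the plan says.** **Protocol 4.11.** When an adverse event is the reason for withdrawal, "the subject should be followed until resolution of that adverse event or determination that the subject's condition is stable". The next sentence reads: "Upon withdrawal from the study, data will cease to be collected on Case Report Forms". It does not exempt the event being followed, and it is not limited to subjects who refuse further data collection; the section also allows the investigator to withdraw a subject. For a subject who wishes to withdraw, a final visit is requested and "a Termination CRF should be completed by the site and provided to the Sponsor".

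**Protocol 5.7.8.** "All unresolved AEs should be followed by the investigator until resolution is reached". Yet safety surveillance and reporting run only until the last visit, death, or the point at which "the subject/investigator concludes his participation into the investigation". SAEs and adverse device effects go to the sponsor within 72 hours of awareness, on the Adverse Event form.

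**Protocol 5.8.1.** All subject deaths are reported within 72 hours of awareness on the Death Form. Withdrawn subjects are not mentioned. Appendix H lists both the Adverse Event and Death forms among the case report forms.

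**SAP 2.5.1 and 2.5.2.** The 30-day numerator is "Number of subjects with at least one event within 30 days post procedure". The 6-month, 1-year and 2-year MACE rates divide by "the number of subjects who experienced an event within or were followed to each time interval". Overall renal vascular safety counts subjects with a serious, device or procedure related event and divides by everyone randomized to denervation. SAP 2.2 includes whatever data are available from withdrawn subjects.

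**The concern.** A site that applies 4.11 literally goes on observing the subject but records nothing. The forms that would carry the information are CRFs, and CRF collection has ended. 5.7.8 does not settle the matter, because it too requires follow-up to resolution while closing reporting when participation ends.

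This can change a planned rate because the status of an event may not be settled at withdrawal. Protocol 5.7.3 defines seriousness by consequences: death, life-threatening illness, permanent impairment, hospitalization, or intervention to prevent such harm. An event that is not serious on the withdrawal date can become so later. The renal vascular safety rate depends on that classification, and the MACE rates depend on whether a qualifying event was recorded within the interval. With about 50 subjects in the denervation arm and purely descriptive reporting, one missed event visibly alters a rate.

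**Working it through.** The documents state no figure on this point, so there is none to reproduce. The check follows one subject through the two protocol rules and the SAP formulas.

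**Inputs**
- Denervation arm: 50, the minimum number treated (Protocol 7.2, SAP 2.2). Taking the number randomized as 50 too is an assumption.
- Number withdrawn with an ongoing event, *k*: not in the documents; 1, 2, 3 and 5 are assumed.
- MACE rate at an interval = subjects with an event / (subjects with an event or followed to the interval) (SAP 2.5.2).
- Renal vascular rate = subjects with a serious related event / all randomized to denervation (SAP 2.5.2). The SAP phrase is read here as serious and related. If any related event counts whatever its seriousness, a recorded related event already qualifies at withdrawal and this rate loses nothing.

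**Case A: the event already qualifies at withdrawal.** It precedes withdrawal, so it is reportable before the stop. The subject stays in numerator and denominator: *k*/50 = 2%, 4%, 6%, 10%. Nothing is lost.

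**Case B: the event is ongoing at withdrawal and qualifies only later, within the interval.** Nothing further is recorded.

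| *k* (assumed) | If captured | MACE rate as recorded | Renal vascular rate as recorded |
|---|---|---|---|
| 1 | 1/50 = 2% | 0/49 = 0% | 0/50 = 0% |
| 2 | 2/50 = 4% | 0/48 = 0% | 0/50 = 0% |
| 3 | 3/50 = 6% | 0/47 = 0% | 0/50 = 0% |
| 5 | 5/50 = 10% | 0/45 = 0% | 0/50 = 0% |

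For MACE the subject has neither a recorded event nor follow-up to the interval, and so leaves both parts of the fraction. For renal vascular safety the subject stays in the denominator and counts as event-free.

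**Short-term rates.** For the 7-day MACE rate, withdrawal and escalation would both have to fall within seven days. The 30-day rate asks only for at least one event, so an event recorded by day 30 would ordinarily count whatever its later course. Both are little affected.

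**Effect of the fix on the MACE denominator.** Suppose three of 50 withdraw and one of them later has a MACE that is now captured. The literal rule gives 0/47 = 0%. The fix gives 1/(47 + 1) = 1/48 = 2.1%. Full follow-up with no other event gives 1/50 = 2.0%. The fix overshoots slightly, because event-free withdrawn subjects remain outside the denominator.

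**The case against.** The strongest reply is that the SAP rates count subjects with events, not how events end. The event that causes withdrawal comes first, falls under the 72-hour rule if it is an SAE or device effect, and keeps its subject in the rate. SAP 2.2 retains available data from withdrawn subjects. That stands, and it rules out a tempting stronger reading: that events leading to withdrawal never reach the safety rates. Case A shows they do.

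A reader might also infer that deaths after withdrawal have no route to the sponsor. Section 5.8.1 covers all subject deaths without exception, so that goes too far; what is unclear is how it fits with the stop in 4.11.

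Nor do the documents support a demonstrated downward bias across the 7-day to 2-year rates, or one that differs by arm. They give no rate of withdrawal for adverse events and no evidence that such subjects are more likely to have a later serious event. The MACE criteria sit in a separate Adverse Event Adjudication Plan.

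The reply does not dispose of Case B. Seriousness is defined by consequences, so outcome can decide whether an event counts. A sentence that includes available data cannot supply data whose collection has stopped. The Kaplan-Meier analysis of MACE is optional, and it would censor these subjects at a time related to their health.

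**Conclusion.** The point holds in a limited form. 4.11 and 5.7.8 each require follow-up of an unresolved event and each close the recording of it, and 5.8.1 is not reconciled with them. The loss is confined to the outcome of events ongoing at withdrawal, and to later worsening that makes such an event serious or a MACE. Each such subject lowers the renal vascular safety rate by one numerator count, or leaves the 6-month, 1-year or 2-year MACE rate altogether: 2 percentage points per subject in an arm of 50.

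That figure assumes 50 subjects, one later qualifying event within the interval, and the serious-and-related reading of the renal rate. How often this would happen cannot be estimated from the documents. It merits correction because sites are already obliged to observe the information being lost.

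**What to change.** 1. In Protocol 4.11, state that, unless the subject withdraws consent to further data collection, the Adverse Event and Death CRFs stay open for events ongoing at withdrawal until they resolve or stabilise.
2. In 5.7.8, align the end of safety reporting with that rule. In 5.8.1, say how it applies to deaths after withdrawal.
3. In SAP 2.5.1 and 2.5.2, count the final seriousness and outcome of these events in the interval in which they occur, and report how many events each rate gains this way.

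**Cost.** Wording changes in both documents, two existing forms left open after the Termination form, and a few more queries. For withdrawals due to an adverse event, 4.11 already requires the follow-up. For other withdrawals with an event ongoing, the duty rests on the general rule in 5.7.8.

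**Limits.** MACE rates may come out slightly high, as in the 1/48 example, which is why the added events should be reported. A new, unrelated MACE after the ongoing event has settled would still not be captured.
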